Section # and Name	Description of Change	Brief Rationale
1.3 Schedule of Activities, Inclusion Criterion #4, 7.2.6 BRAF Testing, CCI [REDACTED]	Clarified BRAF V600 tissue testing by local PCR or NGS-based assay. Optional tumor biopsy added to EOT. Additional serum blood samples will be collected on C1D1, C2D1, C3D1 and EOT.	Serum blood samples will be collected on C1D1, C2D1, C3D1 and EOT for analysis of potential proteomic or metabolomic factors and signatures.
7.3.5. Vital Signs	Vital signs clarified from oral temperature to temperature.	Clarification.
7.3.7. Clinical Safety Laboratory Assessments and Appendix 2 (Recommended Dose Modifications for Encorafenib)	Added the following sentence: "Electrolyte abnormalities including magnesium should be corrected and cardiac risk factors for QT prolongation (e.g., congestive heart failure, bradyarrhythmias) should be controlled."	Additional language required by Health Canada prior to subjects being dosed in Canada.
7.8.1. Blood Sample Collection	Added PK sample schedule Table 13 to be collected from all Phase 2 patients if the high-dose regimen is determined not to be safe, as a result, the original Table 13 was renumbered to Table 14.	If the high-dose is determined not to be safe, PK sample collection will proceed with a reduced PK schedule detailing collection times for the standard dose Arm A.
2.4. Benefit/Risk Assessment, 8.1. Statistical Hypothesis, 8.2. Sample Size Determination, Phase 2, 8.3. Analysis Sets, 8.4. Statistical Analysis, 8.5. Interim Analysis	Interim analysis removed. Sample size determination for Phase 2 revised for the new study design. Table 14 Operating characteristic of the Phase 2 interim analysis has been removed. In Table 15, the Full Analysis Set was updated to only include patients in the randomized Phase 2 (Arms A and B).	The study design was simplified removing the Pick the Winner approach and the interim analysis. Sample size adjusted for new study design. The study design was simplified removing the interim analysis changing the full analysis set. The study design was simplified, and the interim analysis is no longer necessary.
Administrative Change	In some instances, references to Array have been changed to Sponsor.	Responsibility for some study functions has been modified from "Array BioPharma" to the more general "Sponsor" as a result of Array BioPharma, Inc. becoming a wholly owned subsidiary of Pfizer, Inc.

Amendment 1 (08 April 2019)

This amendment modifies the eligibility criterion pertaining to hepatic function to require eligible patients to have total bilirubin $\leq 1.5 \times \text{ULN}$. Per US National Cancer Institute guidelines on classification of hepatic impairment, total bilirubin levels of $\leq 1.5 \times \text{ULN}$ would limit the study population to patients with normal hepatic function or mild hepatic impairment. Patients with elevated bilirubin may be admitted to the study on a case-by-case basis following review and agreement by the Medical Monitor if there is documented

evidence that the elevation is not due to decreased hepatic function, which could affect encorafenib and/or binimetinib exposures.

Section # and Name	Description of Change	Brief Rationale
Protocol Title Page	EudraCT Number is now available and has been added to the title page of the protocol.	To provide the EudraCT Number for the study.
1.3 Schedule of Activities, (SoA) Table 3	ECHO/MUGA assessment on Cycle 1 Day 1 removed.	ECHO/MUGA is performed at Screening and throughout the study. Removal of the Cycle 1 Day 1 ECHO/MUGA avoids the possibility that a patient might undergo these tests in close proximity. This is consistent with other Array-sponsored studies of encorafenib/binimetinib in combination.
5.1 Inclusion Criteria	Inclusion criterion 9e was modified to require eligible patients to have total bilirubin $\leq 1.5 \times$ ULN. Patients with documented Gilbert syndrome or hyperbilirubinemia due to non-hepatic cause may be enrolled following discussion and agreement with the Array Medical Monitor.	This change limits the study population to patients with normal hepatic function or mild hepatic impairment per US NCI guidelines.

1. VERSION HISTORY

Table 1: Summary of Change

Version/ Date	Associated Protocol Amendment	Rationale	Specific Changes
1.0/ 17 June 2020	2.0/ 13 March 2020	Not Applicable	Not Applicable
2.0/ 18 September 2020	3.0/ 07 August 2020	Updates per protocol amendment v3.0; Pfizer SAP template is used and the standard language and methods included in the Pfizer Oncology Statistics Rulebook are adopted	
 1. General – Added data analysis and summary to address COVID-19 related issues. 2. Section 2 – Added explanation that this version of SAP is based on the outcome of the Safety Lead-in that the high-dose treatment of encorafenib was not included in Phase 2. Therefore no randomization is used in Phase 2. 3. Section 4 – Deleted Per-protocol analysis set. CCI [REDACTED] Minor updates on Safety Set and PK Set. 4. Section 5.2 – Added additional information on general methods per Pfizer Oncology Statistics Rulebook. 5. Section 5.2.5 – Updated on-treatment period definition to include all subsequent anticancer therapies (not just anticancer drug therapy). 6. Section 6.2.5 – Updated PFS censoring reasons and hierarchy per Pfizer Oncology Statistics Rulebook. 7. Section 6.3.1 – Revised the list of PK parameters to be estimated and reported, when feasible and appropriate. CCI [REDACTED] 9. Section 6.6 – Deleted body weight, ECOG PS, dermatologic, ECHO/MUGA and ophthalmic examination data descriptive summary per Pfizer TLFs reduction recommendation. Deleted listing of dermatological examination and physical examination as minimum data are collected for these parameters. CCI [REDACTED] 10. Section 6.6.1 – Added AE summary for patients escalating to 600 mg encorafenib in Phase 2.

2. INTRODUCTION

This statistical analysis plan (SAP) provides the detailed methodology for summary and statistical analyses of the data collected in Study C4221006 (ARRAY-818-201). This document may modify the plans outlined in the protocol; however, any major modifications of the primary endpoint and key secondary endpoint definition or corresponding analyses will also be reflected in a protocol amendment.

The study plans to have two parts with Safety Lead-in followed by Phase 2. At the time of this document development, 3 dose-limiting toxicities (DLTs) have been observed in 9 evaluable patients enrolled in the Safety Lead-in of the study. The protocol defines the high-dose regimen of 300mg BID encorafenib + 45mg QD binimetinib combination therapy deemed not safe if 3 DLTs or more (ie, $\geq 33\%$) are observed in 9 evaluable patients in the Safety Lead-in. Therefore the study continues to Phase 2 without the high-dose regimen. The SAP version 2.0 is developed based on this study design scenario, ie, if the high-dose treatment is determined not to be safe in the Safety Lead-in, no patients will be enrolled into the high-dose arm, up to 100 patients will be enrolled into 2 cohorts in the standard-dose arm and no randomization will be used in the Phase 2 part of the study.

2.1. Study Objectives, Endpoints, and Estimands

Primary Objective	Primary Endpoint

Safety Lead-in
 
 Evaluate the safety of a high-dose regimen of encorafenib + binimetinib combination therapy in patients with BRAFV600-mutant melanoma who have asymptomatic brain metastasis. 	
Safety Lead-in
 
 Incidence of DLTs. Incidence and severity of AEs graded according to the NCI CTCAE version 4.03 and changes in clinical laboratory parameters, vital signs and ECGs. Incidence of dose interruptions, dose modifications and discontinuations due to AEs.

Phase 2
 
If the high-dose regimen is determined to be safe based on the results of the Safety Lead-in phase, then
 
 Evaluate the antitumor activity in brain metastases of the standard and high dose regimens of encorafenib + binimetinib combination therapy in patients with BRAFV600-mutant melanoma who have asymptomatic brain metastasis. 	
Phase 2
 
 BMRR per mRECIST v1.1.

If the high-dose regimen is determined not to be safe based on the results of the Safety Lead-in phase, then
 
 Evaluate the antitumor activity in brain metastases of the standard dosing regimen of encorafenib + binimetinib combination in patients with BRAFV600-mutant melanoma who have asymptomatic brain metastasis. 	

Secondary Objectives
	
Secondary Endpoints


 Further evaluate the antitumor activity of encorafenib + binimetinib combination therapy in patients with BRAFV600-mutant melanoma who have asymptomatic brain metastasis. 	
 Extracranial response rate per RECIST v1.1. Global response rate (brain metastasis response per mRECIST v1.1 and extracranial response per RECIST v1.1). DCR: 
 for brain metastasis response per mRECIST v1.1; for extracranial response per RECIST v1.1; for global response (brain metastasis per mRECIST v1.1 and extracranial per RECIST v1.1). DOR: 
 for brain metastasis response per mRECIST v1.1; for extracranial response per RECIST v1.1; for global response (brain metastasis per mRECIST v1.1 and extracranial per RECIST v1.1). PFS: 
 for brain metastasis per mRECIST v1.1; for global assessment (brain metastasis per mRECIST v1.1 and extracranial disease per RECIST v1.1). BMRR per mRECIST v1.1 for Safety Lead-in only.

 Evaluate the efficacy of encorafenib + binimetinib combination therapy as measured by OS in patients with BRAFV600-mutant melanoma who have asymptomatic brain metastasis. 	
 OS.

 Further evaluate the safety profile of encorafenib + binimetinib combination therapy in patients with BRAFV600-mutant melanoma who have asymptomatic brain metastasis. 	
 Incidence and severity of AEs graded according to the NCI CTCAE version 4.03 and changes in clinical laboratory parameters, vital signs and ECGs.

 Characterize the PK of encorafenib and its metabolite LHY746, and binimetinib and its metabolite AR00426032. 	
 Plasma concentration-time profiles and PK parameter estimates for encorafenib and its metabolite LHY746, and binimetinib and its metabolite AR00426032.
CCI [REDACTED]	[REDACTED]
[REDACTED]	[REDACTED]
[REDACTED]	[REDACTED]
[REDACTED]	[REDACTED]
[REDACTED]	[REDACTED]

2.1.1. Primary Estimands

Phase 2

The primary estimand in Phase 2 is the treatment effect of encorafenib + binimetinib combination therapy in confirmed brain metastasis response rate (BMRR) by Investigator assessment per modified Response Evaluation Criteria in Solid Tumors version 1.1 (mRECIST v1.1). The estimand has the following attributes:

- Population: all patients as defined by the inclusion/exclusion criteria in Section 5.1 and Section 5.2 in the study protocol and with a central laboratory confirmed result of *BRAFV600* to reflect the patients targeted by the clinical question.

[REDACTED]

[REDACTED]

- Variable: brain metastasis response defined as best overall response (BOR) of confirmed complete response (CR) or confirmed partial response (PR) in brain metastasis by Investigator assessment per mRECIST v1.1 from date of the first dose until disease progression, death due to any cause, or start of subsequent anticancer therapy, whichever occurs first.
- Intercurrent events: hypothetical strategy will be applied for the intercurrent event of starting new anticancer therapy. Any tumor assessments after starting subsequent anticancer therapy will be excluded in the calculation of BMRR.
- Population-level summary measure: BMRR defined as proportion of patients who have achieved a confirmed BOR of CR or PR in brain metastasis by Investigator assessment per mRECIST v1.1 and corresponding exact Clopper-Pearson 2-sided 90% confidence interval (CI) and 95% CI.

2.1.2. Additional Estimands

Supportive Estimand 1 (BMRR):

- Population: same as primary estimand of BMRR.
- Variable: confirmed + unconfirmed brain metastasis response defined as BOR of confirmed or unconfirmed CR or PR in brain metastasis by Investigator assessment per mRECIST v1.1 from date of the first dose until disease progression, death due to any cause, or start of subsequent anticancer therapy, whichever occurs first.
- Intercurrent events: same as primary estimand of BMRR.
- Population-level summary measure: confirmed + unconfirmed BMRR defined as proportion of patients who have achieved a BOR of confirmed or unconfirmed CR or PR in brain metastasis by Investigator assessment per mRECIST v1.1 and corresponding exact Clopper-Pearson 2-sided 95% CI.

Supportive Estimand 2 (BMRR):

- Population: all patients as defined by the inclusion/exclusion criteria in Section 5.1 and Section 5.2 in the study protocol to reflect the patients targeted by the clinical question.
- Variable: same as primary estimand of BMRR.
- Intercurrent events: same as primary estimand of BMRR.
- Population-level summary measure: BMRR and corresponding exact Clopper-Pearson 2-sided 95% CI.

2.2. Study Design

This is a multicenter, randomized open-label Phase 2 study to assess the safety, efficacy and PK of 2 dosing regimens of encorafenib + binimetinib combination therapy in patients with *BRAFV600*-mutant melanoma with asymptomatic brain metastasis. Approximately 110 eligible patients will be enrolled, including 9 patients in a single-arm Safety Lead-in. After a Screening Period, treatment will be administered in 28-day cycles and will continue until disease progression, unacceptable toxicity, withdrawal of consent, start of subsequent anticancer therapy, death. Once the patient discontinues study treatment, the Treatment Period will end, and the patient will enter the Follow-up Period.

The first 9 evaluable patients in the high-dose treatment will constitute the high-dose Safety Lead-in cohort.

[figure not shown]
As the high-dose treatment is determined not to be safe in the Safety Lead-in, no patients will be enrolled into Arm B, and up to 100 patients will be enrolled into 2 cohorts in the standard-dose Arm A:

- **Cohort 1:** Up to 50 patients with *BRAFV600* cutaneous melanoma with metastases to the brain confirmed by MRI, asymptomatic, and with prior local therapy (eg, stereotactic radiosurgery [SRS] or stereotactic radiotherapy [SRT]).
- **Cohort 2:** Up to 50 patients with *BRAFV600* cutaneous melanoma with metastases to the brain confirmed by MRI, asymptomatic, without prior local therapy (eg, SRS or SRT). Phase 2 enrollment will close when either Cohort 1 or 2 reaches approximately 50 patients.

Patients who are able to tolerate the standard dose of encorafenib (450 mg QD) plus binimetinib (45 mg BID) during the first 4 weeks of treatment (Cycle 1) should be dose-escalated to 600 mg encorafenib QD plus 45 mg binimetinib BID provided they meet the criteria defined in Section 6.7.2 in the protocol.

A schematic of the study design is presented in [Figure 1](#)

Figure 1: Study Schema

3. ENDPOINTS AND BASELINE VARIABLES: DEFINITIONS AND CONVENTIONS

3.1. Safety Lead-in

3.1.1. Primary Endpoint

The primary endpoint for the Safety Lead-in is incidence of DLTs estimated based on data from DLT-evaluable patients during Cycle 1. A DLT is defined as any AE or laboratory abnormality (unexplained by underlying disease, disease progression, intercurrent illness, or concomitant therapies) that either meets the criteria described in the study protocol (Table 7) or results in the inability to tolerate at least 75% of the planned dose of binimetinib or encorafenib during Cycle 1.

3.2. Phase 2

3.2.1. Primary Endpoint

Confirmed BMRR is defined as the proportion of patients who have achieved a BOR of confirmed CR or confirmed PR by Investigator assessment in brain metastasis per mRECIST v1.1.

The definition of BOR is described in [Section 6.1.2](#).

3.2.2. Efficacy Secondary Endpoints

3.2.2.1. Extracranial Response Rate

Extracranial response rate is defined as the proportion of patients with a BOR of confirmed CR or confirmed PR in extracranial lesions by Investigator assessment per Response Evaluation Criteria in Solid Tumors version 1.1 (RECIST v1.1).

3.2.2.2. Global Response Rate

Global response rate is defined as the proportion of patients with a BOR of confirmed CR or confirmed PR by Investigator assessment in brain metastasis and extracranial lesions per mRECIST v1.1 and RECIST v1.1, respectively.

3.2.2.3. Disease Control Rate

Disease control rate (DCR) is defined as the proportion of patients with a BOR of CR, PR or SD by Investigator assessment.

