8.4.2.3. Disease Control Rate

Disease control rate is defined as the proportion of patients with a best overall response of CR, PR or SD per Investigator assessment.

DCR will be calculated for brain metastasis, extracranial and global response along with exact two-sided 95% CIs, respectively.

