Time Point Response

It is assumed that at each protocol-specified time point, a response assessment occurs. Table A1 provides a summary of the overall response status calculation at each time point for patients who have measurable disease at baseline.

Table A1: Time Point Response: Patients With Target (\pm Non-target) Disease

Target Lesions	Non-target Lesions	New Lesions	Overall Response
CR	CR	No	CR
CR	Non-CR/non-PD	No	PR
CR	Not evaluated	No	PR
PR	Non-PD or not all evaluated	No	PR
SD	Non-PD or not all evaluated	No	SD
Not all evaluated	Non-PD	No	NE
PD	Any	Yes or No	PD
Any	PD	Yes or No	PD
Any	Any	Yes	PD

When patients have non-measurable (therefore non-target) disease only, Table A2 is to be used.

Table A2: Time Point Response: Patients With Non-target Disease Only

Non-target Lesions	New Lesions	Overall Response
CR	No	CR
Non-CR/non-PD	No	Non-CR/non-PD ^a
Not all evaluated	No	NE
Unequivocal PD	Yes or No	PD
Any	Yes	PD

a. 'Non-CR/non-PD' is preferred over 'stable disease' for non-target disease since SD is increasingly used as endpoint for assessment of efficacy in some trials so to assign this category when no lesions can be measured is not advised.

Missing Assessments and Inevaluable Designation

When no imaging/measurement is done at all at a particular time point, the patient is not evaluable (NE) at that time point. If only a subset of lesion measurements is made at an assessment, usually the case is also considered NE at that time point, unless a convincing argument can be made that the contribution of the individual missing lesion(s) would not change the assigned time point response. This would be most likely to happen in the case of PD.

Best Overall Response: All Time Points

The *best overall response* is determined once all the data for the patient is known.

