6.1. Primary Endpoints

6.1.1. Safety Lead-in

The number and proportion of patients experiencing DLTs during Cycle 1 will be summarized by SOC and PT based on maximum toxicity grade. Analyses of DLT will be performed on Dose-determining Set.

All DLTs and their attributes will be presented in data listings sorted by patient identifier, AE and date of onset of the AE.

6.1.2. Phase 2

Main Analysis:

BMRR will be calculated by dividing the number of patients with a BOR of confirmed CR or confirmed PR in brain metastasis by the number of patients in the Efficacy Set in the respective cohort. The corresponding exact Clopper-Pearson 2-sided 90% CI and 95% CI will be calculated.

BOR is defined as the best response recorded from date of the first dose of study treatment until progression by Investigator assessment at each time point. Only tumor assessments performed before the start of any subsequent anticancer therapies will be considered in the assessment of BOR. Clinical deterioration or clinical progression noted on the End of Study completion eCRF will not be considered as documented disease progression. BOR will be determined according to the following rules:

- CR = at least two determinations of CR at least 4 weeks apart and documented before progression and start of new anticancer therapy.
- PR = at least two determinations of PR or better (and not qualifying for a CR) at least 4 weeks apart and documented before progression and start of new anticancer therapy.
- SD (for patients with at least one measurable lesion at baseline)= at least one SD assessment (or better and not qualifying for CR or PR) ≥ 6 weeks after date of the first dose and before progression and start of new anticancer.
- Non-CR/Non-PD (for patients with only non-target disease at baseline) = at least one Non-CR/Non-PD assessment (or better and not qualifying for CR or PR) ≥ 6 weeks after date of the first dose and before progression and the start of new anticancer therapy.
- PD = progression ≤ 16 weeks after date of the first dose (and not qualifying for CR, PR or SD).
- Not Evaluable (NE) = all other cases.

The frequency (number and percentage) of patients with BOR in brain metastasis of CR, PR, SD, PD, non-CR/non-PD (applicable only to patients with non-measurable disease at baseline), and NE will be tabulated.

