6.2. Efficacy Secondary Endpoints

6.2.1. Extracranial Response Rate

Extracranial response rate will be calculated by dividing the number of patients with a BOR of CR or PR in extracranial lesions by the number of patients in the Efficacy Set in the respective cohort. The corresponding exact Clopper-Pearson 2-sided 95% CI will be calculated.

Details for the determination of BOR are provided in [Section 6.1.2](#).

Two sets of extracranial response rates will be summarized, one based on confirmed responses and one based on confirmed + unconfirmed responses in extracranial lesions.

Patients with extracranial response rate ‘Not Evaluable’ will be summarized by reason for having unknown status (see [Section 6.1.2](#) for reasons).

A figure for duration of exposure and best overall extracranial response (confirmed) per RECIST v1.1 will be created.

A waterfall plot will be created to show the best percentage change from baseline in the sum of longest diameters of target extracranial lesions. Patients with baseline and at least one post-baseline extracranial tumor assessment will be included in the waterfall plot.

Individual extracranial lesion measurements, overall extracranial response assessments, and target and non-target response by timepoint per RECIST v1.1 will be listed.

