6.2.3. Disease Control Rate

DCR will be calculated for brain metastasis per mRECIST v1.1, extracranial lesion response per RECIST v1.1 and global response along with corresponding exact Clopper-Pearson 2-sided 95% CI.

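### Extracranial disease control rate omits Non-CR/Non-PD, so patients with controlled, non-target-only extracranial disease are in its default denominator but cannot count as controlled unless they reach confirmed CR.

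*SAP*

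**What the plan says.** Both documents define DCR by the same three categories. The SAP wording is "Disease control rate (DCR) is defined as the proportion of patients with a BOR of CR, PR or SD by Investigator assessment" (3.2.2.3). The protocol has "Disease control rate is defined as the proportion of patients with a best overall response of CR, PR or SD per Investigator assessment" (8.4.2.3). SAP 6.2.3 then says "DCR will be calculated for brain metastasis per mRECIST v1.1, extracranial lesion response per RECIST v1.1 and global response", with no further category and no denominator of its own.

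The rules for best overall response (BOR) are in SAP 6.1.2. SD is limited by the words "SD (for patients with at least one measurable lesion at baseline". The next rule is for everyone else: "Non-CR/Non-PD (for patients with only non-target disease at baseline) = at least one Non-CR/Non-PD assessment", at least 6 weeks after first dose and before progression or new anticancer therapy. SAP 6.2.1 carries these rules over to extracranial lesions: "Details for the determination of BOR are provided in" Section 6.1.2.

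Protocol Appendix 4 agrees at the level of the single time point: "When patients have non-measurable (therefore non-target) disease only, Table A2 is to be used". Table A2 has rows leading to CR, Non-CR/non-PD, NE and PD, and none leading to SD or PR.

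**The concern.** The DCR formula was written for patients with measurable disease, but it is also applied to a compartment where measurable disease is not an entry requirement. A patient whose non-target extracranial disease does not progress has controlled disease in the ordinary sense. The formula nevertheless groups that patient with those who progressed or were not evaluable. The extracranial DCR, a listed secondary endpoint, would then depend partly on how many patients happened to have non-measurable disease, and any effect would be downward.

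**Working it through.** The documents give no DCR figure to reproduce, so the check is of definitions, followed by an illustration.

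**1. Which BOR can a non-target-only patient have?** Under SAP 6.1.2 and Table A2: CR, Non-CR/Non-PD, PD or NE. SD and PR need target lesions. The SAP rule for Non-CR/Non-PD also takes in assessments better than that which do not qualify as CR or PR, so an unconfirmed CR falls there too. The only route into the DCR numerator is confirmed CR.

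**2. Can such patients be enrolled?** Yes. Inclusion criterion 6 requires a measurable brain lesion, and no criterion requires measurable extracranial disease. Protocol 7.2.1 treats locally treated extracranial lesions that have not progressed as non-target. Appendix 4 also classes small lesions, nodes of 10 to below 15 mm short axis and blastic bone lesions as non-measurable.

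**3. Are they in the denominator?** By default, yes. SAP Section 4 makes the Efficacy Set the default for efficacy analyses, and SAP 6.2.1 divides extracranial responses by all Efficacy Set patients in the cohort. No rule removes non-target-only patients.

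**4. Are the other compartments affected?** Hardly. Every eligible patient has a measurable brain lesion, and Protocol Appendix 6 pools brain and extracranial target lesions for global response, so SD is normally available in both.

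**5. Size.** Each controlled non-target-only patient without confirmed CR lowers the rate by 100/n points. With n = 50, that is 100/50 = 2 points.

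Illustration, all assumed: n = 50; 80% of patients truly controlled extracranially, both overall and in the non-target-only group; no confirmed CR in that group; counts rounded to whole patients. With Non-CR/Non-PD counted, DCR is 40/50 = 80% (Clopper-Pearson 95% CI 66.3 to 90.0).

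| Non-target-only patients | Of these, controlled | DCR as written (95% CI) | Loss |
|---|---|---|---|
| 0 | 0 | 40/50 = 80% (66.3 to 90.0) | 0 |
| 3 | 2 | 38/50 = 76% (61.8 to 86.9) | 4 points |
| 5 | 4 | 36/50 = 72% (57.5 to 83.8) | 8 points |
| 10 | 8 | 32/50 = 64% (49.2 to 77.1) | 16 points |
| 15 | 12 | 28/50 = 56% (41.3 to 70.0) | 24 points |

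If about one in five of the controlled non-target-only patients reaches confirmed CR, the patients lost are 2, 3, 6 and 10 for the last four rows, and DCR is 76%, 74%, 68% and 60%.

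**The case against.** The strongest defence is that the omission is deliberate. The footnote to Table A2 prefers Non-CR/non-PD because SD is increasingly used as an efficacy endpoint, "so to assign this category when no lesions can be measured is not advised". DCR is such an endpoint, protocol and SAP agree on its definition, and CR + PR + SD is estimated exactly as defined. On that view there is no error, only a stricter target.

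Part of this stands: the two documents do not contradict each other on DCR, and the category should not be relabelled SD. But the footnote is about labels. It does not say that non-progressing patients should be scored as uncontrolled, and neither document states that intent. If DCR is meant to rest on measurable disease only, these patients should leave the denominator as well. As written, they are in the denominator but barred from the numerator except through confirmed CR, so the text needs a change on either view.

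Two further objections stand in full. The consequence is limited: this is one descriptive secondary estimate, with no hypothesis test, and the error cannot inflate the claimed benefit. The alternative rate could also be rebuilt later from the response listings planned in SAP 6.2.1.

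**Conclusion.** The concern holds for the extracranial DCR. The definition and the BOR rules do not fit together, and the mismatch can only lower the estimate. The firm figure is 2 points per affected patient in a cohort of 50. The total rests on a count that the documents do not give, and it is zero if no such patient enrols. That these patients count as failures follows from the Efficacy Set default, since SAP 6.2.3 names no denominator.

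A reader might infer more, in two ways that the documents do not support:

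- **That such patients will be enrolled.** The eligibility criteria and lesion rules show only that they can be.
- **That the extracranial DCR is understated by 5 to 24 points.** That range comes from 0.10 × 0.50 = 0.05 and 0.30 × 0.80 = 0.24, where 10 to 30% is an assumed share with non-target-only disease and 50 to 80% an assumed share of those with Non-CR/Non-PD. The first share refers to patients with extracranial disease, whereas the default denominator is the whole Efficacy Set cohort. If 70 to 90% of the cohort had extracranial disease (also an assumption), the range would be 0.70 × 5 = 3.5 to 0.90 × 24 = 21.6 points.

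The primary BMRR test is not affected, and brain and global DCR are essentially unaffected.

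**What to change.** In SAP 3.2.2.3 and 6.2.3, define DCR as a BOR of CR, PR, SD or Non-CR/Non-PD, with the 6-week minimum that SAP 6.1.2 already sets for the last two. In 6.2.3, also state the denominator for the extracranial DCR, including how patients with no extracranial disease at baseline are handled, since they too remain in the Efficacy Set by default. If the sponsor prefers a rate based on measurable disease, the consistent alternative is to restrict the extracranial DCR to patients with measurable extracranial disease and to say so.

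Protocol 8.4.2.3 should be aligned at the next amendment. A separate amendment does not appear necessary: Protocol Section 8 requires one for major changes to the primary endpoint, SAP Section 2 adds key secondary endpoints, and DCR is not labelled key.

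The cost is a few words in the SAP and a small programming change before database lock. No new data are needed.
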